SBHC	School-based health center
IPW	Inverse probability weighting
MSM	Marginal structural models
GLMM	Generalized linear mixed models
BASICS	Building Adaptive School-based Interventions for Caries Study
NIMHD	National Institute on Minority Health and Health Disparities
SYS	Schoolyard Smiles

Protocol Summary

Title	The Building Adaptive School-based Interventions for Caries Study (BASICS): A phase III sequential, multiple assignment, randomized trial of minimally invasive therapies to reduce treatment nonresponse
Short Title	BASICS
Brief Summary	
School-based caries prevention (SBCP) programs increase access to essential oral healthcare and reduce dental caries, the world's most prevalent noncommunicable disease. However, approximately 1 in 4 children participating in SBCP fail to respond to care, remaining at risk for persistent caries and associated sequelae. The Building Adaptive School-based Interventions for Caries Study (BASICS) is a sequential, multiple assignment, randomized trial of minimally invasive interventions to reduce treatment nonresponse in school caries prevention.
 
BASICS will be conducted in an estimated 1200 children in grades K-3 who are participating in an existing school-based caries prevention program. The SBCP program – known as SCHOOLYARD SMILES (SYS) – is providing all treatments to be tested in the study as part of their standard program procedures. For the study, the sequence of treatments being provided will be altered, with the goal of improving treatment effectiveness and efficiency.
 
Parents or guardians of children who are participating in the SBCP program will consent to participate in the BASICS study, and children will provide assent. Study participants will then be randomly assigned to an initial intervention, after which their treatment responsiveness will be measured and subsequent randomization pathways assigned, resulting in six treatment subgroups forming different adaptive preventive interventions (AI), also known as dynamic treatment regimes (DTR). The study will collect data biannually

Phase	Phase 3
Objectives	
 1. What is the most effective first-stage treatment for caries prevention, assessed via caries incidence? 2. What is the most effective sequence of treatments to reduce treatment nonresponse, assessed via caries incidence? 3. What is the optimal dynamic treatment regime given patient attributes, assessed via varies incidence modified by disease severity, sociodemographics, and treatment history? 4. Given alternative strategies, what is the most cost-efficient allocation of resources that can most significantly affect population health, measured by time and cost of care?
Methodology	Sequential, Multiple-Assignment, Randomized Trial (SMART)
Endpoint	The primary study endpoint is treatment nonresponse, defined as presence/absence of caries and the total number of caries observed.
Study Duration	Five years

Participant Duration	2.5 years
Duration of IP administration	Five years
Population	Our targeted enrollment is 1200 children aged 5-12 years. From prior studies, we anticipate an equal sex allocation, and average age of 7.2 years, predominantly from low-income families. The general health status of the population is healthy.
Study Sites	Schools participating in the Schoolyard Smiles SBCP
Number of participants	1200
Description of Study Agent/Procedure	Treatments include silver diamine fluoride (SDF), fluoride varnish (FV), and resin-modified glass ionomer cement (GIC) sealants to prevent caries. SDF is also provided to arrest caries. GIC can also be used to arrest caries, and when used for this purpose, is called atraumatic restoration, or ART. SDF and ART can also be provided in combination, which is referred to as silver modified atraumatic restorative technique (SMART). We will also provide participants with an electronic toothbrush. For interventions using SDF, one drop (0.05 ml) of SDF solution at 38% concentration (2.24 F-ion mg/dose) will be dispensed per child. Posterior tooth surfaces to be treated will be dried, and the SDF will be applied with a microbrush to all asymptomatic cavitated lesions and to all pits/fissures on bicuspid and molar teeth for 30 s. For interventions using sealants and/or ART, glass ionomer sealants will be applied to all pits and fissures of bicuspid and molars, and placement of ART on all frank asymptomatic cavitated lesions. For Silver Modified Atraumatic Restorative Technique, SDF will be applied as described above on any carious tissue, followed by glass ionomer cement for restoration. Auto-cure GIC will be used to reduce SDF/sealant stain. For FV, a 5% NaF solution will be applied to all teeth after application of SDF or ART.
Reference Therapy	As a sequential, multiple-assignment, randomized trial, there is no reference therapy beyond standard of care (dental sealants), as described above.
Key Procedures	Full-mouth visual-tactile oral examination, SDF application, FV application, dental sealant application.
Statistical Analysis	For objective 1, we will use generalized linear mixed models followed by marginal causal excursion effect estimation. For objective 2, we will use augmented inverse probability weighting (AIPW) with marginal structural models (MSM) and Q-learning. For objective 3, we will use microcosting in tandem with time studies.

Schematic of Study Design

Observation and Treatment Schedule

Observation	Procedures	Estimated Time
0-months (Time 1)	Initial treatment, SDF or sealant	Fall 2026
6-months (Time 2)	Tailoring observation, second line treatment	Spring 2027
12-months (Time 3)	Tailoring observation, second line treatment	Fall 2027
18-months (Time 4)	Outcome Observation	Spring 2028
24-months (Time 5)	Outcome Observation	Fall 2028
30-months (Time 6)	Outcome Observation	Spring 2029

Subgroup Size and Interventions

Subgroup A	N = 420	Silver diamine fluoride (single application)
Subgroup B	N = 90	Silver diamine fluoride (initial treatment) followed by SDF reapplication plus FV plus electronic toothbrushing
Subgroup C	N = 90	Silver diamine fluoride (initial treatment) followed by GIC sealant application and silver modified atraumatic restorations
Subgroup D	N = 420	GIC sealants (single application)
Subgroup E	N = 90	GIC sealants (reapplication, as ART) followed by FV plus electronic toothbrushing
Subgroup F	N = 90	Add SDF as silver modified atraumatic restorative treatment

1 Key Roles

Principal Investigator

[name] [name], MPH; Associate Professor
New York University
[name]
[name]
[contact]
[contact]

Clinical Director (Sub-Investigator)

[name] [name], MPH; Research Scientist
New York University
[name]
[name]
[contact]
[contact]

Research Scientist (Sub-Investigator)

[name]; Assistant Professor
New York University
[name]
[name]
[contact]
[contact]

Site PI

To Be Determined

NIH Program Director

[name]
Supervisory Team Lead, Integrative Biological and Environmental Sciences
National Institute on Minority Health and Health Disparities
[name]
[contact]
[contact]

2 Introduction, Background Information and Scientific Rationale

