Nonresponse will be determined at the second and third post-baseline observational periods by the diagnosis of any dental caries on posterior dentition, including any new caries on previously sound dentition (primary prevention failure) or any teeth diagnosed at baseline with caries that failed to demonstrate arrest (secondary prevention failure). The total number of caries will also be recorded. Responders to either first stage treatment will continue to receive biannual screenings for retention and responsiveness. Non-responders will subsequently proceed to second-stage randomization.

Nonresponders in Trajectory 1 will receive a second-stage randomization to either SDF reapplication plus fluoride varnish receipt of an electronic toothbrush, or an SDF reapplication plus dental sealants. As nonresponse is determined by the diagnosis of new caries, this latter pathway will take the form of delayed silver-modified atraumatic restorative treatment (delayed SMART) [22, 23] on any affected teeth and application of sealants to any remaining sound dentition. Similarly, nonresponders in Trajectory 2 will be randomized to either an augmented treatment of sealant reapplication (including atraumatic restorations) plus fluoride varnish and receipt of an electronic toothbrush or an intensified protocol of SMART on affected dentition. Caries incidence will continue to be evaluated at each remaining planned observation.

Additional design procedures include (1) any patients with sealants that are not retained but no decay is indicated will be considered responsive and the sealant will be reapplied; (2) any patients with atraumatic restorations that are not retained will be considered non-responsive, as it cannot be robustly determined if there is no new decay; (3) any responding participant who transitions to nonresponse after the predetermined nonresponse periods will continue to receive their original first-stage intervention and the total days that elapsed before nonresponse was observed will be recorded; (4) any nonresponding patient who continues to fail to respond will receive reapplication/reinforcement of their second-stage intervention; (5) any new dentition that erupts in either Phase 1 or Phase 2 will receive the corresponding treatment for that phase (e.g., first-stage or second-stage randomized treatment).

7.1.2

Standard of Care Study Procedures

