7.3 Study Schedule

All of the visits described below are part of the research study. Study participants are still part of the school-based caries prevention program at the same time.

7.3.1

Screening

Screening (Day -28 to -1)

- Obtain informed consent of potential participant verified by signature on written informed consent for screening form.
- Review medical history to determine eligibility based on inclusion/exclusion criteria.
- Review dental history to determine eligibility based on inclusion/exclusion criteria.
- Schedule study visits for participants who are eligible and available for the duration of the study.

7.3.2

Enrollment/Baseline

Enrollment/Baseline Visit (Visit 1, Day 0)

- Obtain informed consent of potential participant, if not obtained in Screening period
- Verify inclusion/exclusion criteria.
- Perform comprehensive oral examination
- Administer the study treatment following first-stage randomization (See Figure 1):
 - Either silver diamine fluoride or glass ionomer cement sealants

7.3.3

Intermediate Visits

7.3.3.1 Visit 2

(Day 160-200)

- Record adverse events as reported by participant or observed by investigator.
- Perform comprehensive oral examination
- Record patients responsiveness status
- Proceed with second stage randomization if determined by comprehensive examination to be in treatment nonresponse (See Figure 1)
- Administer relevant treatment as indicated by second stage randomization

7.3.3.2 Visit 3

(Day 340-380)

- Record adverse events as reported by participant or observed by investigator.
- Perform comprehensive oral examination

- Record patients responsiveness status
- Proceed with second stage randomization if determined by comprehensive examination to be in treatment nonresponse (See Figure 1)
- Administer relevant treatment as indicated by second stage randomization

7.3.3.3 Visit 4

(Day 520-560)

- Record adverse events as reported by participant or observed by investigator.
- Perform comprehensive oral examination
- Document clinical outcomes
- Maintain treatment as indicated in Subgroup (Figure 1)

7.3.3.4 Visit 5

(Day 700-740)

- Record adverse events as reported by participant or observed by investigator.
- Perform comprehensive oral examination
- Record patients responsiveness status
- Document clinical outcomes
- Maintain treatment as indicated in Subgroup (Figure 1)

7.3.4

Final Study Visit

Final Study Visit (Visit 6, Day 880-920)

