10.2 Statistical Hypotheses

The null hypothesis is that there is no difference in treatment nonresponse between first stage assignments (SDF compared to dental sealants). The alternative hypothesis is that they are different. The study is a superiority trial. Endpoints will be evaluated at the end of the treatment nonresponse observational window (Study visit 3) and at the completion of subsequent visits (Study visit 4, 5, and 6).

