10.4 Description of Statistical Methods

10.4.1

General Approach

BASICS is a phase-III Sequential, Multiple Assignment, Randomized Trial (SMART) (described fully in the Schematic of Study Design). Descriptive statistics will use percentages and counts for persons with dichotomous outcomes and means/standard deviations for continuous outcomes. For inferential tests, the p-value used for statistical significance (Type 1 error) is 0.05, and all tests are two-tailed.

10.4.2

Analysis of the Primary Efficacy Endpoint(s)

The primary efficacy endpoints include the best initial treatment for dental caries and the best treatment sequence for nonresponders. This is equivalent to the main effect of the first-stage treatment and additional clinically-relevant contrasts (see Statistical Analysis Plan for further description). Data will be analyzed according to intent to treat. The main effects will be assessed using generalized linear mixed logistic regression (for presence/absence of dental caries and presence/absence of treatment nonresponse) and negative binomial regression (for caries incidence). Predictors include semester of entry, the interaction between semester and treatment trajectory, and any relevant demographic variables. Any instance of missing data will be accounted for using time-ordered nested conditional imputation.

10.4.3

Analysis of the Secondary Endpoint(s)

Secondary endpoints in BASICS include the best dynamic treatment regime, the optimal adaptive intervention, and costs of adaptive interventions. Analysis for the best adaptive intervention will utilize weighting and replication and other methods (see Statistical Analysis Plan). Analyses for identifying the optimal adaptive intervention will use Q-Learning (see SAP).

For cost analyses, we will quantify the economic costs of dynamic treatment regimes in school-based caries prevention will using microcosting in tandem with time studies. We will take a bottom-up microcosting approach to data collection. The bottom-up approach to microcosting is characterized by quantifying resource utilization for each cost item, and then aggregating to the individual or system-level, as opposed to assessing system costs and then allocating to individual cost items (top-down approach).⁷³ This approach is more accurate for labor-intensive services than microcosting with a top-down approach.⁷⁴⁻⁷⁶ We will use the following tools to capture costs:

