10.5 Sample Size

Sample size calculations for Objective 1 are computed for the main effects of the specified experimental design, including the main effects for first-stage treatment (A+B+C vs D+E+F) and the main effects for second-stage treatment in nonresponders (B+E vs C+F). These main effects are equivalent to a longitudinal comparison of two parallel groups in a randomized trial [45]. We assume a within-person correlation of 0.5, a study drop-out rate of 10% (with the difference offset by newly enrolled children each year), a desired power of 0.85, and an alpha of 0.05. This yields a total sample size of 122 for a medium effect size (Cohen's $d=0.5$). As a result, our anticipated

sample size is sufficient for even small to medium effects at acceptable power levels. We subsequently propose sampling more subjects to support investigation of effect modifiers or subgroup comparisons (e.g., A+B, A+C, D+E). For second-stage treatment main effects, additional considerations are needed for the rate of nonresponse [45]. We assume nonresponse rates are equal across first-stage treatment assignments, and further assume an average nonresponse rate of 30% (as informed by prior studies). This yields a total N of $122/0.3 = 406$, or N=203 for first-stage treatment groups and 101 in each nonresponse group (B+E and C+F).

For Objective 2, we estimate power based on the Multiple Comparisons with the Best (MCB) methodology for comparing our embedded DTRs while accounting for multiple comparisons, thereby increasing power [46]. We assume a type 1 error rate, now viewed as the probability of excluding the best DTR from the set of all DTRs, of 5%. We estimate the expected power given our anticipated final sample size assuming the same 10% yearly dropout rate (N=840) for four DTRs, with a minimum effect size of 0.1: $Power_{\alpha,n}(\Sigma, \Delta, \Delta_{min}) \geq 1 - \beta$. We assume the most conservative case as possible by setting all other DTRs to be the minimum detectable effect size away, compared to DTR(1) ($\Delta_i = \Delta_{min}$). We also assume that correlations between DTRs are equal, in keeping with recommendations. This yields a power of >99%, and the study is well powered even for exceedingly small effect size differences. Finally, as optimization using Q-learning is considered hypothesis generating in the SMART framework, we do not estimate power for this analysis.

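### The main-effects predictors stated in 10.4.2 omit the visit at which a nonresponder was re-randomized (6 or 12 months), which costs the pooled B+E vs C+F contrast some precision and leaves it exposed if allocation changes between the two visits

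*Protocol*

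**What the plan says.** **Two start times.** The Observation and Treatment Schedule gives "Tailoring observation, second line treatment" for both 6 months (Time 2) and 12 months (Time 3). Sections 7.3.3.1 (Visit 2, Day 160-200) and 7.3.3.2 (Visit 3, Day 340-380) carry the same instruction: "Proceed with second stage randomization if determined by comprehensive examination to be in treatment nonresponse". The Schedule of Events marks randomization at both visits. Section 7.1.1 words it differently: "Nonresponse will be determined at the second and third post-baseline observational periods". Read literally, those are Visits 3 and 4, so the passages need reconciling. On either reading there are two windows six months apart.

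**One pooled contrast.** Section 10.5 counts among the main effects "the main effects for second-stage treatment in nonresponders (B+E vs C+F", and adds: "These main effects are equivalent to a longitudinal comparison of two parallel groups in a randomized trial".

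**Reading times.** Section 10.2, after stating the first-stage hypothesis, says: "Endpoints will be evaluated at the end of the treatment nonresponse observational window (Study visit 3) and at the completion of subsequent visits"; the visits it then names are 4, 5 and 6.

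**Model.** Section 10.4.2 counts the best treatment sequence for nonresponders among the primary efficacy endpoints. It assesses the main effects by mixed logistic and negative binomial regression. On covariates it says: "Predictors include semester of entry, the interaction between semester and treatment trajectory, and any relevant demographic variables". In 7.1.1 a trajectory is the first-stage arm, and semester of entry is when the child joined the study. Neither identifies the visit of re-randomization. For additional contrasts 10.4.2 refers to the statistical analysis plan, which is not at hand.

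**Allocation.** Section 10.6.1 calls the randomization adaptive and individual-level. It does not define the type or mention stratification by visit.

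**The concern.** A child who fails at Visit 2 and one who fails at Visit 3 enter the same second-stage comparison with different histories. The first has six more months of second-line treatment at every later visit and, having failed sooner, probably develops new caries faster. The visit of re-randomization is therefore likely to predict the outcome. It is fixed before second-stage assignment and is already recorded, so it is an obvious adjustment variable for B+E vs C+F, yet the stated predictors leave it out.

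Two things are at stake. The first is precision: variation between early and late failures stays in the residual. The second is validity, and it is conditional. If the chance of being assigned to B or E rather than C or F differs between Visits 2 and 3, the two pooled arms hold different shares of early failures. The unadjusted contrast then partly compares early with late failure. The protocol does not say that this happens, but it leaves the adaptive scheme undefined and so does not exclude it.

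**Working it through.** **1. The plan's own figure.** Section 10.5 gives a total of 122 (d = 0.5, power 0.85, two-sided alpha 0.05, within-person correlation 0.5, 10% dropout). A two-sample t calculation needs 73 per arm, 146 in total. Taking the correlation to enter as a variance factor of 1 - 0.5² = 0.75, 146 × 0.75 / 0.9 = 121.7, which rounds to 122. The normal approximation gives 144 × 0.75 / 0.9 = 120. Then 122 / 0.3 = 406.7, against the stated 406. The figure reproduces. It has no input for two start times.

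**2. Second-line exposure at common visits** (from the observation schedule).

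| Visit | Re-randomized at Visit 2 | Re-randomized at Visit 3 |
|---|---|---|
| 4 (18 months) | 12 months | 6 months |
| 5 (24 months) | 18 months | 12 months |
| 6 (30 months) | 24 months | 18 months |

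**3. Assumptions, none given in the protocol.** Share s of nonresponders found at Visit 2: 0.5-0.7. New lesions per year: 0.8-1.0 in early failures, 0.5-0.8 in late failures. Negative binomial dispersion 1, so variance = μ + μ². Results are on the count scale.

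**4. Precision, constant allocation.** Extra residual variance from omitting the visit = s(1-s)(μ₂-μ₃)² / [s·v₂ + (1-s)·v₃], where subscripts 2 and 3 are the visit of re-randomization.

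- *Visit 4, lesions counted from re-randomization* (1.0 vs 0.5 years). High end, s = 0.5, μ = 1.0 and 0.25: 0.25 × 0.5625 / (0.5 × 2.0 + 0.5 × 0.3125) = 0.122. Low end, s = 0.7, μ = 0.8 and 0.4: 0.21 × 0.16 / (0.7 × 1.44 + 0.3 × 0.56) = 0.029. Range 3-12%.
- *Visit 6, same clock* (2.0 vs 1.5 years): 1-11%.
- *Visit 4, counted from baseline* (1.5 years for both). High end, μ = 1.5 and 0.75: 0.25 × 0.5625 / (0.5 × 3.75 + 0.5 × 1.3125) = 0.056. Low end 0, when both rates are 0.8. Range 0-6%.
- *Per six-month interval.* High end, μ = 0.5 and 0.25: 0.25 × 0.0625 / (0.5 × 0.75 + 0.5 × 0.3125) = 0.029. Range 0-3%.

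The counting rule matters as much as the assumed rates, so the summary is roughly 0-12%.

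**5. Bias, constant allocation.** The early-failure share is s in both pooled arms, so the expected imbalance is zero.

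**6. Bias if allocation moves from 50:50 at Visit 2 to 60:40 at Visit 3.** This shift is hypothetical.

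- s = 0.5: late-failure share is 0.30 / 0.55 = 0.545 in one arm and 0.20 / 0.45 = 0.444 in the other, a gap of 0.101.
- s = 0.7: 0.18 / 0.53 = 0.340 and 0.12 / 0.47 = 0.255, a gap of 0.084.

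Multiplying by μ₂ - μ₃ at Visit 4, counted from re-randomization: 0.101 × 0.75 = 0.076 and 0.084 × 0.40 = 0.034 lesions. Against overall means of 0.625 and 0.68 that is 12% and 5%. At Visit 6 the same steps give 0.03-0.13 lesions (2-9%). Counted from baseline, the Visit 4 figure runs from 0 to 0.08.

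**7. A rate-free check.** With equal failure hazard in both windows and 30% nonresponse in total, s = (1 - √0.7) / 0.3 = 0.544. If one arm received 40% at Visit 2 and 60% at Visit 3, early failures would be 44% of that arm and 64% of the other. A prognostic gap of 0.5 SD would then give 0.20 × 0.5 = 0.10 SD of bias.

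**The case against.** The best defence has four parts.

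- **Where the model is stated.** B+E vs C+F is spelled out only in the sample-size section. The visit list in 10.2 follows a hypothesis about first-stage arms. The predictor list in 10.4.2 opens with a word that need not be exhaustive, and further contrasts are left to the analysis plan. This stands in part: the unseen plan may already contain the term. But 10.4.2 does name predictors for the main effects, and 10.5 counts this contrast as one.
- **No bias under constant allocation.** This stands in full. Children are randomized at whichever visit they fail, so the early/late mix is balanced in expectation.
- **Fixed visits are legitimate.** Averaging over 6- and 12-month starts is what the regimes deliver. A reader might infer that reading at common visits is an error, because under linear accrual the pooled Visit 4 effect is 0.5 + 0.5 × 0.5 = 75% of the 12-month effect when half fail at Visit 2. That describes a different estimand. Replacing the clock would compare early failures at Visits 3-5 with late failures at Visits 4-6, mixing semester, age and eruption, so it is a trade-off and not a correction.
- **Power is ample.** With 840 retained, 840 × 0.3 / 2 = 126 per pooled arm. Power is then 0.996 at d = 0.5 if the effect is constant once treated. This stands.

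Two further inferences are not supported. Section 10.6.1 does not say that second-stage assignment is stratified by visit; randomizing at two visits is not stratification. And the likeness to two parallel groups in 10.5 is a sizing analogy that needs no common start, so removing it would change no result.

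**Conclusion.** The point holds as a modest gap in the stated model. Re-randomization takes place at two visits six months apart, and the predictors named for the main effects do not carry that visit. Under constant allocation the pooled B+E vs C+F contrast remains unbiased, and the cost is roughly 0-12% extra residual variance under assumed rates, with the upper part of that range applying only if lesions are counted from re-randomization. Confounding by early versus late failure arises only if allocation differs between Visits 2 and 3. The protocol neither states nor rules that out; a 50:50 to 60:40 shift would produce up to about 0.08 lesions at Visit 4 and 0.13 at Visit 6.

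A reader might go further and conclude that the second-stage estimate is biased, that the study is underpowered for it, or that the fixed reading visits are wrong. The document supports none of these. The sizes above rest on assumed failure timing, lesion rates, dispersion and allocation shift.

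**What to change.** In 10.4.2, for the B+E vs C+F contrast, add first-stage arm, visit of re-randomization (Visit 2 or Visit 3) and their interaction to the logistic and negative binomial models. This removes the early/late variation from the residual, and it protects the contrast if allocation differs by visit.

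Keep the fixed study visits as the reading times. A comparison at 6, 12 and 18 months since re-randomization may be reported as supportive. Every nonresponder has those visits scheduled: Visits 3-5 after re-randomization at Visit 2, and Visits 4-6 after Visit 3.

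The cost is a sentence of analysis text and one derived variable, with no new visits or data. The model spends a few degrees of freedom, and its odds ratio is then conditional on these strata, which the report should say. If the analysis plan already contains the term, 10.4.2 need only be aligned with it.
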